## 3.3 STUDY AREA

The location of the training and test will be conducted at Beijing Sport University's North Gymnasium, a 'Fédération International de Gymnastique' -certified facility equipped with:

1. Olympic-grade balance beams (10 cm width, 5 m length).
2. Spring floors (Ariake, Japan) for jump training.
3. Climate-controlled environment (20–22°C, 50–60% humidity).

### **3.4 STUDY POPULATION**

The target population for this study is newly registered female university students (aged 18 to 22), who are enrolled in the gymnastic class as part of their physical education degree programme.

### **3.5 SUBJECT CRITERIA**

#### **3.5.1 Inclusion criteria**

The inclusion criteria for the study population are as follows:

1. Females
2. Age ranged between 18 -22 years old, normal body mass index (BMI) (18.5 -25kg/m^2) (Traczyk et al., 2023).
3. Undergraduate students of physical education at Beijing Sport University.
4. No prior systematic gymnastics training (or with  $\leq$  1 year of systematic training experience), and no history of congenital diseases or musculoskeletal injuries.

#### **3.5.2 Exclusion Criteria**

1. Participants suffering from acute or chronic musculoskeletal injuries (lasting for 6 months or more), neurological disorders (such as epilepsy), or vestibular dysfunction.
2. Ranked athletes or elite athletes.
3. Participants with poor compliance (< 80%) who are unable to complete the 8 - week exercise intervention program.
4. Individuals who have recently undergone or are scheduled to undergo surgery within three months.

### **3.5.3 Withdrawal Criteria**

Participation in this study is entirely voluntary. Participants may refuse to participate in this study or stop participating in this study at any time without penalty or loss of benefits to which they are otherwise entitled. An example of this would be if a subject develops an illness during the intervention. The research team may also stop their participation without their consent if they breach the study eligibility criteria in any way.

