### **3.2.1.2 Tests and Training Plan Schedule for the Experimental Group**

The test protocols and training components for stability and jumping skills were derived from outcome measures in an unpublished systematic review and deemed appropriate following discussions with [name], a gymnastics coach at Beijing Sport University. Thus, Table 9 and 10 present the stability and jumping test programme to be conducted, table 11 outlines the 8-week training schedule for the experimental group participants.

Table 9: Stability and Jumping Test Programme

Test items	Testing time	Testing content	Testing Instruments
Stability test	Baseline Measurement End of experiment week 8 test	8 Point Star Offset	Star Excursion Balance Test
Jumping test	Baseline Measurement End of experiment week 8 test	1. Countermovement Jump 2. Single-leg countermovement Jump	Force Plate

Table 10: Gymnastic Performance Movements

Test items	Testing time	Testing content	Testing Instruments
Standing Single-leg 360 ° turn	Baseline Measurement End of experiment week 8 test	Standing Single-leg 360 ° turn	3D motion capture technology
Straight jump 360 ° turn	Baseline Measurement End of experiment week 8 test	Straight jump 360 ° turn	3D motion capture technology

[figure not shown]
Table 11: Experimental Training group

Training Programme	Routine Training	Group1 (Static balance training)	Group2 (Dynamic balance training)	Group3 (Static and Dynamic balance training)
Week 1				
baseline test				
Week 2-3				
•Activity/Mode		Basic Adaptation Period		
•Duration	• 90 minutes/per session	•15 minutes/ session	•15 minutes/ session	•30 minutes/ session
•Intensity (Heart rate)	• 100bpm-160bpm	• 80bpm-100bpm	• 90bpm-110bpm	• 90bpm-110bpm
•Inter-group Rest Duration	• 2 minutes	• 2 minutes	• 2 minutes	• 2 minutes
Week 4				
•Activity/Mode	The same content	①Eyes-closed double-leg stance ②Plank support	①Jumping onto a low balance beam ②Half squat exercise	①Jumping onto a low balance beam + Walking on the Balance Beam + Landing control training ②Half Squat Exercise + Throwing - catching ball exercise
•Duration	• 90 minutes/per session	•15 minutes/ session	•15 minutes/ session	•30 minutes/ session
•Intensity (Heart rate)	• 100bpm-160bpm	• 80bpm-110bpm	• 90bpm-110bpm	• 90bpm-110bpm
•Inter-group Rest Duration	• 2 minutes	• 2 minutes	• 2 minutes	• 2 minutes
Week 5				

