### **3.8 INTERVENTION METHODS**

Participants in the SG intervention group will complete an 8-week training program consisting of Plank Support, Single-Leg Stance, Eyes-Closed Double-Leg Stance, and Half-Squat Exercise. The DG intervention group will engage in Landing Control Training, Balance Beam Walking, jumping onto the Balance Beam, and Squat-to-Stand Exercises. The SDG intervention group will perform Plank Support, Single-Leg Stance, Eyes-Closed Double-Leg Stance, Half-Squat Exercise, Landing Control Training, Balance Beam Walking, jumping onto the Balance Beam, and Squat-to-Stand Exercises. Each exercise will be repeated 3 times or the corresponding number of times per session, with each session lasting 15 minutes (including 30 minutes of dynamic and static balance exercises), conducted twice a week for 8 weeks. All participants will enroll simultaneously, and each group will be guided by qualified instructors. Before and after each training session, participants will wear a heart rate monitor (Xiaomi Smart Band) on their wrist to ensure adherence to the prescribed training intensity outlined in Tables 13, 14, and 15. Additionally, participants may adjust their limb positions and movement intensity based on their physical condition. At the end of each session, training logs will be completed to document the activities. Only data from participants who adhere to at least 80% of the prescribed training program will be included in the analysis.

Participants in the control group (CG) will continue their regular training routine as detailed in Tables 7 and 8. They will be advised to maintain their usual daily activities without incorporating any additional exercises.

Table 13: Static balance training intervention content (n=15)

Week	content	Minutes/ Groups	Inter-group Rest Duration	Training duration	HR Monitoring Indicators	Heart Rate Monitoring Equipment	Intervention time	Heart rate range	Equipment
W 1	baseline test								
W 2-3	①Double leg stand ②Single leg stand	1/3	Rest for 2 minutes	15minutes	Resting Heart Rate (Before Training)/Maxi mum Heart Rate/Maximum Heart Rate	Xiaomi Smart Band	8 weeks, 2 times per week, 15 minutes each time	80bpm-100bpm	Balance board、BOSU ball
W 4	①Eyes-closed double-leg stance ②Plank support	1/3	Rest for 2 minutes	15minutes				80bpm-110bpm	Balance board 、 BOSU ball、 Gymnastic mat

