## **5.4 ETHICAL CONSIDERATIONS**

### **5.4.1 Subject vulnerability**

In this study, participants may experience mild symptoms such as muscle fatigue, slight dizziness, or balance instability during the intervention. However, these symptoms typically subside within 24–48 hours after completing the training or testing. If participants experience any discomfort, appropriate medical care and interventions will be provided as needed.

Throughout the training and testing period, participants' safety will be closely monitored.

Medical laboratory officers and technicians trained in cardiopulmonary resuscitation (CPR) and basic life support (BLS) will always be on standby to ensure timely responses to any emergencies. Participants are free to withdraw from the study at any time without any obligations or penalties.

If these symptoms occur, they should immediately stop training and rest as needed. In the event of acute symptoms during the intervention, medical treatment will be promptly provided. Should a participant's condition worsen to the extent that hospitalization is required, the training will be suspended and resumed only after the participant's condition stabilizes. If the condition continues to deteriorate and medical professionals deem the participant unfit to continue, they will be excluded from the study to ensure their safety. The research team is committed to providing a safe environment and a supportive framework to safeguard the health and well-being of all participants throughout the study.

The participant will not be subjected to coercion or deception. All participants in this study are voluntary.

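### Low compliance with training, known only after randomisation, is listed as an exclusion criterion and also removes participants from the analysis (Protocol 3.5.2, 3.5.3, 3.8)

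*Protocol*

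**What the plan says.** Four statements in the Protocol bear on this.

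- **3.5.2 Exclusion Criteria, item 3** excludes "Participants with poor compliance (< 80%) who are unable to complete the 8 - week exercise intervention program".
- **3.5.3 Withdrawal Criteria** states: "The research team may also stop their participation without their consent if they breach the study eligibility criteria in any way".
- **3.8 Intervention Methods** states: "Only data from participants who adhere to at least 80% of the prescribed training program will be included in the analysis".
- **3.8, on the control group**: controls carry on with the routine in Tables 7 and 8, and "They will be advised to maintain their usual daily activities without incorporating any additional exercises".

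Tables 9 and 10 (3.2.1.2) set the test times as "Baseline Measurement End of experiment week 8 test". They do not mention participants who have stopped training. Section 3.6 plans 15 participants per arm and a 15% dropout that it takes to be the same in every group. Section 5.4.1 covers medical events: training interrupted by hospitalisation can resume, and if "medical professionals deem the participant unfit to continue, they will be excluded from the study to ensure their safety".

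**The concern.** An exclusion criterion should be checkable before random allocation. Item 3 is not: nobody has a compliance figure until the training is under way. Because it sits among the eligibility criteria, the broad wording of 3.5.3 turns it into a ground for removing someone already randomised. The adherence rule in 3.8 separately keeps low compliers out of the analysis.

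Item 3 refers to the exercise intervention, which only the static, dynamic and combined arms receive. Removal under it therefore depends on allocation. If those who cannot keep up also improve less, each training arm is left with its better responders while the control arm stays whole. The comparison is then no longer between the groups as randomised, and its error favours training. The uniform dropout assumed in 3.6 does not fit such a rule.

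**Working it through.** **1. When the 80% line is crossed.** Tables 13 to 15 show training in weeks 2 to 7, twice a week: 6 × 2 = 12 sessions.

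| Sessions planned | Missed | Adherence | Kept by 3.8? |
|---|---|---|---|
| 12 | 1 | 11/12 = 92% | yes |
| 12 | 2 | 10/12 = 83% | yes |
| 12 | 3 | 9/12 = 75% | no |
| 16 (if all 8 weeks count, as the text of 3.8 says) | 3 | 13/16 = 81% | yes |
| 16 | 4 | 12/16 = 75% | no |

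**2. How many could be removed.** The protocol gives no non-compliance rate. Its only related figure is the 15% dropout allowance: 0.15 × 15 = 2.25 per arm. That allowance is for all causes and includes controls, so 2 of 15 per training arm is used here as a ceiling, not an estimate.

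**3. Shift in the training-versus-control contrast.** Assumptions: change scores are standard normal with no true effect; the k participants with the lowest value of an index are removed from each training arm and none from control; the index has correlation ρ with change; ρ is 0.3 or 0.5 (assumed, not in the protocol). Then

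shift = ρ × (sum of the k largest expected order statistics of 15 standard normals) / (15 − k).

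The two largest expected values are 1.736 and 1.248.

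- k = 1: 1.736 / 14 = 0.124. Times ρ: 0.037 (ρ = 0.3) and 0.062 (ρ = 0.5).
- k = 2: (1.736 + 1.248) / 13 = 0.230. Times ρ: 0.069 and 0.115.

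A simulation of 200,000 trials per setting gives 0.037, 0.062, 0.070 and 0.116, so the range is about 0.04 to 0.12 SD of change. If the same number is removed from every arm, the expected shift is zero.

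**4. False positive rate, nominal 5%.** The same simulation, using the one-way F test on change (equivalent to the time × group test with two time points):

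| Removed | ρ | Training arms only | All four arms |
|---|---|---|---|
| 1 of 15, overall test | 0.3 | 5.3% | 5.2% |
| 1 of 15, overall test | 0.5 | 5.7% | 5.6% |
| 2 of 15, overall test | 0.3 | 5.5% | 5.3% |
| 2 of 15, overall test | 0.5 | 6.5% | 6.0% |
| 2 of 15, one unadjusted training-versus-control contrast | 0.3 | 5.5% | 5.2% |
| 2 of 15, one unadjusted training-versus-control contrast | 0.5 | 6.6% | 5.7% |

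Arm dependence by itself adds about 0.1 percentage points to the overall test with 1 removed and 0.2 to 0.5 with 2 removed. For the single contrast, with differences taken before rounding, it adds about 0.3 to 0.8.

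**5. Power is not the main issue.** The stated 52 is reproduced with f = 0.35, four groups, two measurements and a pre-post correlation of 0 (assumed; the text gives none): noncentrality = 0.35² × 52 × 2 = 12.74 on 3 and 48 degrees of freedom, power 0.831. Then 52 × 1.15 = 59.8, giving the planned 60. On the same basis, power is 0.889 with all 60 analysed and 0.823 with 51 (60 × 0.85). The harm is mainly selection, not lost power.

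**The case against.** **The adherence rule in 3.8 does most of the damage.** While it stands, 3.5.3 costs no further data on low compliers. This is right, and it is why changing 3.5.2 and 3.5.3 alone would not be enough.

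**Loss of the week 8 test.** A reader might infer that stopping participation cancels the final test. The documents do not say so. Section 3.5.3 gives a permission, Tables 9 and 10 do not limit week 8 testing to compliers, and the flow chart (Figure 2) is not shown. What stands is only that no visible text protects the test.

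**Overlap of the two routes.** A reader might also infer that 3.8 excludes everyone stopped under 3.5.3. It does not. Someone stopped for a new injury after 10 of 12 sessions is at 83% and stays in the analysis.

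**Arm dependence.** The prescribed programme in 3.8 could be read to include the controls' own routine, so only item 3 is clearly confined to the training arms. Item 3 can also be read as needing both low compliance and failure to complete, which would mostly describe people who have already dropped out. Both readings are possible, and neither makes item 3 a usable screening criterion.

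**Section 5.4.1.** It is tempting to count its safety clause as a further arm-dependent exclusion. The text does not support that: the clause is not worded by arm, controls also train, and it concerns participants whose condition keeps deteriorating, who would rarely be fit for jump and turn tests. Nor do the mild symptoms it lists normally lead to removal, since "these symptoms typically subside within 24–48 hours after completing the training or testing", or about one missed session. After hospitalisation, "the training will be suspended and resumed only after the participant's condition stabilizes".

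**Comparison between training modes.** The research questions centre on these. If removal is equal across the three training arms, the mean shift cancels between them. That is fair, but equality is not assured: the combined arm trains 30 minutes per session and the other two 15.

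**Conclusion.** The point holds in a limited form. The protocol places a post-randomisation event among its exclusion criteria, makes any eligibility breach a ground for stopping participation, and states an analysis rule that omits low compliers. Followed as written, this allows a selected comparison that can favour training over control.

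The size cannot be derived from the protocol and is probably small: about 0.04 to 0.12 SD of change, resting on an assumed correlation of 0.3 to 0.5, an assumed direction (low compliers improve less), 1 or 2 of 15 removed per training arm, and no removals from control. The case for acting is that the rule is plainly misplaced, nothing caps the number removed, and the remedy costs almost nothing if made before data collection.

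**What to change.** 1. **3.5.2:** delete item 3.
2. **3.8:** make the main analysis all randomised participants with week 8 data, each in her allocated arm. Keep the set with at least 80% adherence as a secondary analysis.
3. **3.5.3:** keep the power to stop training for safety or for a newly acquired exclusion condition, such as an injury or scheduled surgery. State that low compliance is not a ground for removal, and that every randomised participant who is willing and medically able still does the week 8 tests.

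Changes 2 and 3 belong together. Without 2, retained week 8 data would not reach the main result; without 3, nothing in the visible text secures those data. Leave the safety clause in 5.4.1 as it is.

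**Cost:** edits to three sections, with no extra participants or procedures, since the week 8 tests are already scheduled. Including those who trained less may dilute the estimated effect of full training; the secondary set still shows that effect.

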### **3.6 Sample Size Estimation**

Using G - power 3.1 (Figure 10), the study focuses on time (within - subject factor), group (between - subject factor), and their interaction effects. The effect size is set to medium (0.35), with an alpha value of 0.05 and a statistical power of 0.80. A total of four groups will be included (static balance, dynamic balance, combined static and dynamic balance, and a control group), with measurements conducted twice, pre - and post - intervention. The calculated sample size is 52 participants. Considering a dropout rate of 15%, 60 participants will be recruited. Participants will be randomly assigned to four groups, with 15 participants in each group. Since the total dropout rate applies uniformly and participants are equally distributed across the four groups, each group's dropout rate is also 15%.

[figure not shown]

Figure 10 Flow chart of the G-power

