### 4.0 EXPECTED RESULTS

#### 4.1 Anthropology

Table 16 Height, weight, and BMI at baseline and after 8 weeks in the static, dynamic, static and dynamic intervention and control groups. Data presented as mean  $\pm$  SD.

Anthropometry	Groups								Two-way repeated measures ANOVA					Bonferroni ( $p$ )		
	Static		Dynamic		Static + Dynamic		Control									
	B	W8	B	W8	B	W8	B	W8	SS	df	MS	F	$p$			
Height																
Weight (kg)																
BMI ( $\text{kg}/\text{m}^2$ )																

B= Baseline, W=Week, ANOVA= Analysis of variance; SS=Sum of squares; df= degrees of freedom, MS=Mean square, F= F-test statistical value,  $p<0.05$

denotes significance difference

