### 4.3 Stability test results

Table 18 Eight-point Star Offset stability test results at baseline and 8 weeks postintervention in the static intervention, dynamic intervention, static-dynamic intervention, and control groups. Data presented as mean  $\pm$  SD.

Group	Test Type	Time Point	Anterior reach	posteromedial reach	composite score	Two-Way Repeated Measures ANOVA	Bonferroni (p)
Static balance group	SEBT(Pre-Test)	B					
		W8					
	SEBT(Post-Test)	B					
		W8					
Dynamic balance group	SEBT(Pre-Test)	B					
		W8					
	SEBT(Post-Test)	B					
		W8					
Static and Dynamic balance group	SEBT(Pre-Test)	B					
		W8					
	SEBT(Post-Test)	B					
		W8					
Control group	SEBT(Pre-Test)	B					
		W8					
	SEBT(Post-Test)	B					
		W8					

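### The planned two-wave group-by-time ANOVA is valid, but it is less precise than ANCOVA on the week-8 value with baseline as covariate unless the pre-post correlation is about 0.95 or higher

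*Protocol*

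**What the plan says.** Section 3.6 (Sample Size Estimation) states that "the study focuses on time (within - subject factor), group (between - subject factor), and their interaction effects", "with measurements conducted twice, pre - and post - intervention". The baseline is therefore one of two responses. The inputs are "The effect size is set to medium (0.35"), "with an alpha value of 0.05 and a statistical power of 0.80", and the result is "The calculated sample size is 52 participants", raised to 60 for dropout. On allocation: "Participants will be randomly assigned to four groups, with 15 participants in each group".

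The empty result tables in chapter 4 match this. Table 18 (section 4.3) has a column headed "Two-Way Repeated Measures ANOVA" beside a Bonferroni column, and Tables 17, 19 and 20 are laid out the same way. Table 16 (height, weight, BMI) is headed "Two-way repeated measures ANOVA".

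Section 3.8.3 (Data analysis) lists descriptive statistics, demographic analysis, correlation and factor analysis. It names no model for comparing the arms, neither ANOVA nor ANCOVA. Adjustment for baseline appears nowhere in the protocol. Each tabulated outcome is measured at baseline and at week 8, so the covariate is already collected.

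**The concern.** Baseline is measured before training starts, so in a randomised trial training cannot affect it. Treating it as a second response has three consequences.

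- With two waves, the group-by-time F is identical to a one-way ANOVA on week 8 minus baseline. Subtracting the whole baseline adds its noise whenever the pre-post correlation is below 1. It also over-corrects chance baseline differences, which are not small with about 13 per arm.
- The group main effect averages the untreated baseline with week 8, so a training effect enters at half its size.
- The time main effect does not compare arms.

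Section 3.6 lists all three effects without saying which one decides. What is at stake is precision in a small four-arm trial, and a clear statement of which result is the training effect.

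**Working it through.** **Inputs.** From section 3.6: alpha 0.05, power 0.80, f = 0.35 (read as Cohen's f), 4 equal groups, 2 measurements, N = 52 (13 per arm). The pre-post correlation rho is not in the text, and the G*Power figure is not shown. It is therefore an assumption, taken over a range.

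**Step 1: the plan's own figure.** In G*Power's scaling, the within-between interaction has lambda = f² × N × 2/(1−rho) on 3 and N−4 df.
- rho = 0: lambda = 0.1225 × 52 × 2 = 12.74, power 0.831. The next smaller balanced size, N = 48, gives 0.794. So N = 52 reproduces.
- rho = 0.5: N = 28 is enough (power 0.828).

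The between-groups test also gives 52 at rho = 0, and needs 72 at rho = 0.5.

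**Step 2: variance.** With a common SD at both waves, in units of SD²:
- change score: 2(1−rho)
- ANCOVA residual: 1−rho²
- ratio ANCOVA/change: (1+rho)/2

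Estimating the baseline slope inflates the ANCOVA contrast variance by 1 + 1/46 = 1.022 at 13 per arm (48 within-arm df, less 2). The finite-sample ratio is (1+rho)/2 × 47/46. It reaches 1 at rho = 2 × 46/47 − 1 = 0.957.

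**Step 3: power with the effect set so that the interaction has exactly 80% at N = 52.** On 3 and 48 df this needs lambda = 11.83. ANCOVA has lambda = 11.83 divided by the variance ratio, on 3 and 47 df.

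| rho | ratio, large sample | ratio, 13 per arm | ANCOVA power, large-sample ratio | ANCOVA power, 13 per arm |
|---|---|---|---|---|
| 0.3 | 0.65 | 0.66 | 94.5% | 94.0% |
| 0.5 | 0.75 | 0.77 | 90.7% | 90.1% |
| 0.7 | 0.85 | 0.87 | 86.5% | 85.7% |
| 0.9 | 0.95 | 0.97 | 82.1% | 81.2% |

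A simulation with 13 per arm (4,000 runs) gave interaction against ANCOVA power of 0.80 v 0.94, 0.80 v 0.91, 0.80 v 0.86 and 0.80 v 0.83 at rho 0.3, 0.5, 0.7 and 0.8. Type I error was about 5% for both tests.

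**Step 4: power at the stated f = 0.35, same scaling, N = 52** (ANCOVA with the 13-per-arm ratio).

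| rho | interaction lambda | interaction power | ANCOVA power |
|---|---|---|---|
| 0 | 12.74 | 83.1% | 98.8% |
| 0.3 | 18.20 | 94.5% | 99.4% |
| 0.5 | 25.48 | 99.0% | 99.9% |
| 0.7 | 42.47 | above 99.9% | above 99.9% |

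Both tests reach the ceiling because f = 0.35 is a large effect on this scale. Writing S for the SD of the arm mean changes in outcome SDs, f² × 2/(1−rho) = S²/(2(1−rho)), so S = 2f = 0.70. The 80% calibration at rho = 0.5 corresponds to S = √(11.83 × 2 × 0.5/52) = 0.48.

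**Step 5: the group main effect.** The two-wave mean carries half the effect and has variance (1+rho)/2, so lambda = 11.83 × (1−rho)/(1+rho). Under the step 3 calibration, power is 51%, 33%, 19% and 9% at rho 0.3, 0.5, 0.7 and 0.9.

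**Step 6: chance imbalance.** The baseline difference between two arms of 13 has SD √(2/13) = 0.39 outcome SDs. For an imbalance of that size at rho = 0.5, the change score over-corrects by (1−0.5) × 0.39 = 0.20 SD. ANCOVA, with the slope estimated, does not over-correct on average.

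**The case against.** The strongest reply is that nothing here is an error. Under randomisation the group-by-time test is unbiased and holds its type I error, so the choice is between two valid analyses. That stands. A reader might infer that the planned analysis is biased or invalid, and the protocol does not support that.

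Second, the size of the gain depends on the effect assumed. At the protocol's own f = 0.35 in G*Power's scaling, the gain at rho = 0.5 is from 99.0% to 99.9%. This also stands, and step 3 should be read as showing the gain for smaller effects.

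Third, ANCOVA is not free and not better at every correlation. It spends one degree of freedom, assumes a linear slope, and gains nothing above about rho = 0.95. It also adjusts only for the measured baseline. Section 3.8 restricts the analysis to participants with at least 80% adherence, so imbalance in the analysed set need not be pure chance, and ANCOVA cannot be said to remove it.

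Fourth, the planned model is inferred from the sample-size text and the table headings, because section 3.8.3 names none. Some outcomes in the research questions, such as the SEBT symmetry index, have no table column. It would therefore be too strong to say that every outcome is planned this way.

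Fifth, section 3.6 does not make the group main effect the efficacy test. A reader might infer that the trial rests on the low powers in step 5, but the text does not say so. They only show why that effect should not be read as the training effect.

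A separate statistical analysis plan may exist. The point concerns the model that this protocol already fixes.

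**Conclusion.** The point holds as a matter of efficiency. The planned interaction test is sound but gives away precision that the collected baselines would supply at any correlation below about 0.95. With 13 per arm, the contrast variance under ANCOVA is lower by about 34%, 23%, 13% and 3% at rho 0.3, 0.5, 0.7 and 0.9. In power, this is worth roughly 14, 10, 6 and 1 points for an effect that the interaction would detect with 80% power. It is worth little at f = 0.35 once rho is 0.5 or more. The case is strongest at rho near 0, the value that reproduces N = 52 (83% against 99%).

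These figures assume equal SDs at both waves, a common linear baseline slope, 13 analysed per arm and an assumed rho. The gain is real for moderate correlations, but its size in this trial cannot be fixed from the document. It would be wrong to conclude that the planned analysis is invalid or that ANCOVA is superior at every correlation.

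**What to change.** - In section 3.8.3, name ANCOVA as the between-arm analysis of the hypothesis outcomes: week-8 value as response, arm as factor, baseline value of the same measure as covariate.
- Align section 3.6 and the headings of Tables 17-20 with that model.
- Report baseline-adjusted pairwise arm differences with 95% confidence intervals, and put the Bonferroni-adjusted p values on those differences.
- State that the group and time main effects are not read as training effects.
- Leave Table 16 (height, weight, BMI) descriptive. The repeated-measures ANOVA may stay as a supporting analysis.

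The cost is a change of wording and table headings, with the same data and the same SPSS software. Statistically, it costs one residual degree of freedom (47 instead of 48) and an assumed common linear baseline slope, with no gain if rho is very high. Table 22 dates data collection 1/9/2026, after the protocol date of 25/9/25, so on that timetable the change can be specified before any outcome is measured.

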### **1.3 RESEARCH QUESTIONS**

- (1) What are the differential effects of static, dynamic, and static-dynamic combined balance training on the stability (measured by the maximum distance of single-leg extension and the bilateral symmetry index in the Star Excursion Balance Test (SEBT)) of beginner gymnasts?
- (2) Do static, dynamic, combined balance training induce distinct improvements in jumping mechanics (CMJ/SLCMJ: jump height, PF, RFD, impulse) and kinetic efficiency (jump height/GRF ratio), and does combined training show superior neuromuscular adaptations?
- (3) Among static, dynamic, and static-dynamic combined balance training modalities, which one most effectively minimizes the center of mass (COM) offset distance, body sway amplitude, and landing impact force—while maximizing rotational smoothness and single-leg balance duration—in beginner gymnasts when they perform 360° single-leg standing pirouettes and 360° straight-body jump turns, with all outcomes quantified by 3D motion capture technology?

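### Section 3.6 gives one 0.80 power for time, group and interaction at a medium effect of 0.35, but at N = 52 the group effect falls short for any pre-post correlation above about 0.08, and 0.35 for the interaction means an arm gap of at least 1.4 SD

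*Protocol*

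**What the plan says.** Protocol section 3.6 (Sample Size Estimation) reports a G-Power 3.1 calculation and says that "the study focuses on time (within - subject factor), group (between - subject factor), and their interaction effects". No one of the three effects is singled out as the basis for the sample size. A single set of inputs follows: "The effect size is set to medium (0.35), with an alpha value of 0.05 and a statistical power of 0.80". There are four groups, "with measurements conducted twice, pre - and post - intervention". The result is 52 participants, and then "Considering a dropout rate of 15%, 60 participants will be recruited", with 15 per group.

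The text does not give the pre-post correlation or the effect-size option chosen in the software, and it does not express 0.35 as a difference on any outcome. Figure 10, which belongs to this calculation, is not available in the text at hand.

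The research questions in section 1.3 compare the programmes with one another, for example "does combined training show superior neuromuscular adaptations". The results tables in Chapter 4 provide for a two-way repeated-measures ANOVA and a Bonferroni column.

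**The concern.** In a pre-post design the correlation between the two measurements moves the tests in opposite directions. A higher correlation makes differences in change easier to detect, so it helps time and interaction. It also makes the average of a person's two scores more variable, so it hurts the group main effect. One effect size and one N can therefore carry the same power for group and interaction only when the correlation is zero. That is hard to expect when the same person repeats the same test at baseline and in week 8.

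The second issue is the label. The protocol calls 0.35 *medium* without saying what it means in outcome units. For an interaction with two time points it implies a large separation between arms. A reader of a null result could take it as evidence, backed by 80% power, against a moderate difference, when the calculation assumed a much bigger one. A reader could also assume that the group effect had been powered at 0.80.

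**Working it through.** **Inputs from section 3.6:** f = 0.35, alpha 0.05, power 0.80, k = 4 groups, m = 2 measurements, N = 52. **Assumption:** the pre-post correlation rho, not stated in the text, examined from 0 to 0.8.

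**Formulas** (G-Power default for repeated measures, noncentral F):
- Group: lambda = f² × N × m / (1 + rho), df 3 and N − 4.
- Time: lambda = f² × N × m / (1 − rho), df 1 and N − 4.
- Interaction: same lambda as time, df 3 and N − 4.

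**Step 1: reproduce 52.** At rho = 0, f² × N × m = 0.1225 × 52 × 2 = 12.74 for both group and interaction. With df 3 and 48 this gives power 0.831. At N = 48, lambda is 11.76 and power 0.794. So 52 is the first multiple of four that reaches 0.80. At rho 0.1 the group effect needs 56 and the interaction 48, so with these inputs the match holds for a correlation of zero. The software's other effect-size options need 100 (SPSS option) or 96 (Cohen option) for the interaction, so 52 does not come from them.

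**Step 2: power at N = 52 and f = 0.35 as rho varies.**

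| rho | lambda, group | power, group | power, interaction | N for 0.80 on group |
|---|---|---|---|---|
| 0 | 12.74 | 0.83 | 0.83 | 52 |
| 0.1 | 11.58 | 0.79 | 0.87 | 56 |
| 0.3 | 9.80 | 0.71 | 0.94 | 64 |
| 0.5 | 8.49 | 0.64 | 0.99 | 72 |
| 0.7 | 7.49 | 0.58 | above 0.99 | 80 |

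Power for time is at least 0.938 throughout. Power of exactly 0.80 with df 3 and 48 needs lambda of about 11.83, so the group effect falls below 0.80 once 12.74 / (1 + rho) is less than 11.83, that is, from rho of about 0.08. If all 60 recruited participants complete, group-effect power is 0.785 at rho 0.3, 0.719 at 0.5 and 0.658 at 0.7.

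**Step 3: what f = 0.35 means for the interaction.** With two time points, f² is the mean over arms of ((arm mean change − overall mean change) / 2)², in outcome-SD units. The root-mean-square spread of arm mean changes is then 2 × 0.35 = 0.70 SD. The gap between the highest and lowest arm depends on the pattern:
- two arms against two: 0.70 × 2 = 1.40 SD;
- one arm against three: 0.70 × 4 / √3 = 1.62 SD;
- two extreme arms with two in the middle: 0.70 × √8 = 1.98 SD.

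The smallest possible gap is 1.40 SD. A simulation with 13 per arm and a two-against-two gap of 1.4 SD agrees: interaction power is 0.824 at rho 0 and 0.990 at rho 0.5, and group power is 0.828 and 0.658.

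**Step 4: what 52 can detect at 0.80 power on the interaction.** The detectable f is √(11.83 × (1 − rho) / 104), and the two-against-two gap is 4f:
- rho 0: f = 0.337, gap 1.35 SD;
- rho 0.5: f = 0.238, gap 0.95 SD;
- rho 0.7: f = 0.185, gap 0.74 SD.

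For one arm against three, the gap is 1.10 SD at rho 0.5 and 0.85 SD at rho 0.7.

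**The case against.** The strongest reply is that section 3.6 merely lists the factors of a mixed ANOVA and that one test, presumably the interaction, was selected in the software. Figure 10 may show this, along with the correlation. That is possible, and the missing figure is not held against the plan. The text as written still attaches one power to three named effects, and a reader who has only the text cannot tell otherwise.

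It can also be said that the group main effect matters little here. It averages baseline and follow-up, so it dilutes any training effect. The between-arm question rests on the interaction, which has at least 0.83 power at f = 0.35 for every correlation of zero or more. This stands, and it limits the harm. It also means that nothing is lost by dropping the claim for the group effect.

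Two stronger readings are tempting. A reader might infer that the trial can detect only very large differences. The documents do not support this. The 1.4 SD is what f = 0.35 represents, not what 52 participants can detect, and at a correlation of 0.7 a two-against-two gap of about 0.74 SD is within reach. A reader might also infer that the pairwise comparisons have a specific low power. The Chapter 4 tables show only a Bonferroni column and the number of comparisons is not given, so a pairwise power figure would rest on an assumed count. What can be said is that the calculation does not address those comparisons.

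Finally, the protocol cites no convention for *medium*, so the label cannot be shown to break a stated rule. The objection to it is that it hides an assumed gap of at least 1.4 SD.

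**Conclusion.** The concern holds in a limited form. The figure of 52 is not an arithmetic slip: it reproduces at a correlation of zero. What is wrong is the scope of the power statement and the description of the effect. At f = 0.35, time and interaction have at least the stated power at any correlation of zero or more. The group effect does not: its shortfall is under one percentage point at a correlation of 0.1, and about 9, 16 and 22 points at 0.3, 0.5 and 0.7. The assumed interaction effect is a gap of at least 1.4 SD in mean change.

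These results rest on the stated inputs, G-Power's default parameterisation and assumed correlations. If Figure 10 shows that only the interaction was selected, the group-effect part becomes a matter of wording, while the point about the size of 0.35 remains.

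**What to change.** Rewrite section 3.6 without changing N:
- State that the 0.80 power applies to the time-by-group interaction only.
- Give the pre-post correlation used and the arm difference in SD that the effect size implies, with the pattern of arms assumed (for f = 0.35, 1.40 SD for two arms against two).
- Remove the word *medium* and the power claim for the group main effect.
- Add a sentence saying that the calculation does not cover pairwise comparisons between arms.

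The cost is a few sentences of wording and a narrower stated power claim. Recruitment, arms and analysis are unaffected.
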